4.4. End of Study Definition

The end of the study is defined as the date of the last scheduled procedure shown in the [SoA](#) for the last participant in the trial.

A participant is considered to have completed the study if they have completed all periods of the study, including the last scheduled procedure shown in the [SoA](#).

5. STUDY POPULATION

This study can fulfill its objectives only if appropriate participants are enrolled, including participants across diverse and representative racial and ethnic backgrounds. If a prescreening tool is utilized for study recruitment purposes, it will include collection of information that reflects the enrollment of a diverse participant population including, where

permitted under local regulations, age, sex, race, and ethnicity. The following eligibility criteria are designed to select participants for whom participation in the study is considered appropriate. All relevant medical and nonmedical conditions should be taken into consideration when deciding whether a particular participant is suitable for this protocol.

Prospective approval of protocol deviations to recruitment and enrollment criteria, also known as protocol waivers or exemptions, is not permitted.

5.1. Inclusion Criteria

Participants are eligible to be included in the study only if all of the following criteria apply:

Age and Sex:

1. Females of non-childbearing potential and males 18 to 65 years of age, inclusive, at the time of signing the ICD who are overtly healthy as determined by medical evaluation including medical history, physical examination, laboratory tests, and cardiac monitoring.
 - Refer to [Appendix 4](#) for reproductive criteria for male ([Section 10.4.1](#)) and female ([Section 10.4.2](#)) participants.

Other Inclusion Criteria:

2. BMI of 16-30.5 kg/m²; and a total body weight >50 kg (110 lb).
3. Willing and able to comply with all scheduled visits, treatment plan, laboratory tests, lifestyle considerations, and other study procedures.
4. Capable of giving signed informed consent as described in [Appendix 1](#), which includes compliance with the requirements and restrictions listed in the ICD and in this protocol.

5.2. Exclusion Criteria

Participants are excluded from the study if any of the following criteria apply:

Medical Conditions:

1. Evidence or history of clinically significant hematological, renal, endocrine, pulmonary, gastrointestinal, cardiovascular, hepatic, psychiatric, neurological, or allergic disease (including drug allergies, but excluding untreated, asymptomatic, seasonal allergies at the time of dosing).
 - Any condition possibly affecting drug absorption (eg, gastrectomy, cholecystectomy).

- History of HIV infection, hepatitis B, or hepatitis C; positive testing for HIV, HBsAg, or HCVA. Hepatitis B vaccination is allowed.
- 2. Any medical or psychiatric condition including recent (within the past year) or active suicidal ideation/behavior or laboratory abnormality or other conditions or situations related to COVID-19 pandemic that may increase the risk of study participation or, in the investigator's judgment, make the participant inappropriate for the study.

Prior/Concomitant Therapy:

- 3. Use of prescription or nonprescription drugs and dietary and herbal supplements within 7 days or 5 half-lives (whichever is longer) prior to the first dose of study intervention, with the **CCI** [REDACTED] which are prohibited within 14 days plus 5 half-lives prior to the first dose of study intervention. Refer to [Section 6.9](#) Prior and Concomitant Therapy for additional details.

Prior/Concurrent Clinical Study Experience:

- 4. Previous administration with an investigational product (drug or vaccine) within 30 days (or as determined by the local requirement) or 5 half-lives preceding the first dose of study intervention used in this study (whichever is longer). Participation in studies of other investigational products (drug or vaccine) at any time during their participation in this study.

Diagnostic Assessments:

- 5. A positive urine drug test.
- 6. Screening supine BP ≥ 140 mm Hg (systolic) or ≥ 90 mm Hg (diastolic) for participants < 60 years; and $\geq 150/90$ mm Hg for participants ≥ 60 years old, following at least 5 minutes of supine rest. If systolic BP is ≥ 140 or 150 mm Hg (based on age) or diastolic ≥ 90 mm Hg, the BP should be repeated 2 more times and the average of the 3 BP values should be used to determine the participant's eligibility.
- 7. Renal impairment as defined by an eGFR < 75 mL/min/1.73m². Since participants are 18 years to 65 years, 2021 CKD-EPI eGFR (combined Screat and Scys) is the recommended formula (see [Section 10.7.2](#)) to determine eligibility and to provide a baseline to quantify any subsequent kidney safety events.
- 8. Standard 12-lead ECG that demonstrates clinically relevant abnormalities that may affect participant safety or interpretation of study results (eg, QTcF > 450 ms, complete LBBB, signs of an acute or indeterminate- age myocardial infarction, ST-T interval changes suggestive of myocardial ischemia, second- or third- degree AV block, or serious bradyarrhythmias or tachyarrhythmias). If QTcF exceeds 450 ms, or QRS exceeds 120 ms, the ECG should be repeated twice and the average of the 3 QTcF or QRS values used to determine the participant's eligibility.

Computer-interpreted ECGs should be overread by a physician experienced in reading ECGs before excluding a participant.

9. Participants with ANY of the following abnormalities in clinical laboratory tests at screening, as assessed by the study specific- laboratory and confirmed by a single repeat test, if deemed necessary:

- ALT, AST, total bilirubin $\geq 1.05 \times$ ULN; participants with a history of Gilbert's syndrome may have direct bilirubin measured and would be eligible for this study provided the direct bilirubin level is \leq ULN.

Other Exclusion Criteria:

10. History of alcohol abuse or binge drinking and/or any other illicit drug use or dependence within 6 months of Screening. Binge drinking is defined as a pattern of 5 (male) and 4 (female) or more alcoholic drinks in about 2 hours. As a general rule, alcohol intake should not exceed 14 units per week (1 unit = 8 ounces [240 mL] beer, 1 ounce [30 mL] of 40% spirit, or 3 ounces [90 mL] of wine).
11. Use of tobacco or nicotine-containing products in excess of the equivalent of 5 cigarettes/day or 2 chews of tobacco/day.
12. Investigator site staff directly involved in the conduct of the study and their family members, site staff otherwise supervised by the investigator, and sponsor and sponsor delegate employees directly involved in the conduct of the study and their family members.

5.3. Lifestyle Considerations

The following guidelines are provided:

5.3.1. Contraception

The investigator or their designee, in consultation with the participant, will confirm that the participant is utilizing an appropriate method of contraception for the individual participant and their partner(s) from the permitted list of contraception methods (see [Appendix 4, Section 10.4.4](#)) and will confirm that the participant has been instructed in its consistent and correct use. The investigator or designee will advise the participant to seek advice about the donation and cryopreservation of germ cells prior to the start of study intervention, if applicable.

At time points indicated in [SoA](#), the investigator or designee will inform the participant of the need to use highly effective contraception consistently and correctly and document the conversation and the participant's affirmation in the participant's chart. Participants need to affirm their consistent and correct use of at least 1 of the selected methods of contraception, considering that their risk for pregnancy may have changed since the last visit.

In addition, the investigator or designee will instruct the participant to call immediately if the selected contraception method is discontinued and document the requirement to use an alternate protocol-specified method, including if the participant will no longer use abstinence as the selected contraception method, or if pregnancy is known or suspected in the participant or partner.

5.3.2. Meals and Dietary Restrictions

- Participants must abstain from all food and drink (except water) at least 4 hours prior to any safety laboratory evaluations and approximately 10 hours prior to the collection of the predose PK sample.
- Noncaffeinated drinks (except grapefruit or grapefruit-related citrus fruit juices-see below) may be consumed with meals and the evening snack.
- Lunch will be provided approximately 4 hours after dosing.
- Dinner will be provided approximately 9 to 10 hours after dosing.
- An evening snack may be permitted.
- Participants will refrain from consuming red wine, grapefruit, or grapefruit-related citrus fruits (eg, Seville oranges, pomelos, fruit juices) from 7 days prior to the first dose of study intervention until collection of the final PK blood sample.
- While participants are confined, their total daily nutritional composition should be approximately 55% carbohydrate, 30% fat, and 15% protein, with the exception of dosing days in which a high-fat/high-calorie meal will be given prior to study intervention. The daily caloric intake per participant should not exceed approximately 3200 kcal.
- On non-dosing days while inpatient, as appropriate, standard morning meal, lunch, and evening meal (along with an evening snack) are to be provided at a similar clock time to the clock time when these meals are offered on the dosing day.
- Dosing under fasted conditions:
 - Following an overnight fast of at least 10 hours, participants will receive study intervention.
 - Water is permitted until 1 hour prior to study intervention administration. Water may be consumed without restriction beginning 1 hour after dosing.

- Dosing if food effects are investigated:
 - Following an overnight fast of at least 10 hours, participants should start breakfast approximately 30 minutes prior to administration of study intervention.
 - The high-fat, high-caloric breakfast will be consumed over approximately a 20-minute period with study intervention administered approximately 10 minutes after completion of the meal at 0H.
 - There are no water restrictions prior to dosing for participants dosed under fed conditions. Water may be consumed without restriction beginning 1 hour after dosing.
 - The breakfast will be a high-fat (approximately 50% of total caloric content of the meal), high-calorie (approximately 800 to 1000 calories) meal. The meal will consist of approximately 150 protein calories, 250 carbohydrate calories, and 500-600 fat calories. An example test meal would be: 2 eggs fried in butter, 2 strips of bacon (or 50 g of meat or sausage), 2 slices of toast with butter, 4 ounces (approximately 112 grams) of hash brown potatoes, and 8 fluid ounces (240 mL) of whole milk. Participants will be encouraged to consume the entire meal.

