Continuous cardiac telemetry			X	→	→	→	→	→	→	X				• Baseline telemetry to be recorded for at least 2 hours prior to the first dose in Period 1 only. This may be done immediately prior to dosing or at some 2-hour continuous interval in the 24 hours prior to dosing, as long as the participant is awake. Post-dose telemetry will continue for 8 hours after dosing. See Section 8.3.4.1 for additional information.
Triplet 12-Lead ECG	X	X	X	X	X	X	X	X	X	X				• Triplet measures are collected approximately 2-4 minutes apart. See Section 8.3.4 for additional details.
Triplet Supine BP			X	X	X	X	X	X	X	X				• Triplet measures are collected approximately 2-4 minutes apart. See Section 8.3.3 for additional information.
Temperature, pulse rate and respiratory rate			X			X			X					• See Section 8.3.3 for additional information.
Study intervention administration			X											• Participants should fast for at least 10 hours prior to dosing, except for periods in which food effects are investigated. Dosing under fasted or fed conditions is to occur as outlined in Section 5.3.2 .
Blood sampling for:														
PF-07293893 PK			X	X	X	X	X	X	X	X				• See Section 8.5 for additional details.
Sample for specified protein research			X			X		X		X				• To be collected as outlined in Section 8.7.2 .
Sample for transporter biomarker(s)			X		X	X		X		X	X			• See Section 8.7.5 for additional details.

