8.3.3.3. Temperature

Temperature will be measured orally. No eating, drinking, or smoking is allowed for 15 minutes prior to the measurement.

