8.3.4. Electrocardiograms

Standard 12-lead ECGs will be collected at times specified in the [SoA](#) section of this protocol using an ECG system that automatically calculates the HR and measures PR, QT, QTcF, and QRS intervals. All scheduled ECGs should be performed after the participant has rested quietly for at least 5 minutes in a supine position.

Triplet 12-lead ECGs (as specified in the [SoA](#)) will be obtained approximately 2 to 4 minutes apart; the average of the triplicate ECG measurements collected at -1.0, -0.5, and 0 hours pre-dose on Day 1 of each period will serve as each participant's baseline QTcF value for that period.

To ensure safety of the participants, a qualified individual at the investigator site will make comparisons to baseline measurements. Additional ECG monitoring will occur if a) the mean value from the triplicate measurements for any post-dose QTcF interval is increased by ≥ 60 ms from the baseline and is >450 ms; or b) an absolute QT value is ≥ 500 ms for any scheduled ECG. If either of these conditions occurs, then a single ECG measurement must be repeated at least hourly until QTcF values from 2 successive ECGs fall below the threshold value that triggered the repeat measurement.

For single ECG collections, additional ECG monitoring will occur if a) a postdose QTcF interval is increased by ≥ 60 ms from the baseline and is >450 ms; or b) an absolute QT value is ≥ 500 ms for any scheduled ECG. If either of these conditions occurs, then 2 additional

ECGs will be collected approximately 2 -4 minutes apart to confirm the original measurement. If the QTcF values from these repeated ECGs remain above the threshold value, then a single ECG must be repeated at least hourly until QTc values from 2 successive ECGs fall below the threshold value that triggered the repeat measurement.

If a) a post-dose QTcF interval remains ≥ 60 ms from the baseline and is >450 ms; or b) an absolute QT value is ≥ 500 ms for any scheduled ECG for greater than 4 hours (or sooner, at the discretion of the investigator); or c) QTcF value get progressively longer, the participant should undergo continuous ECG monitoring. A cardiologist should be consulted if QTcF values do not return to less than the criteria listed above after 8 hours of monitoring (or sooner, at the discretion of the investigator).

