3.1.3. Vital Signs

Single supine blood pressure will be measured at screening, follow-up visit and early termination (ET; if applicable). Triplicate supine measurements will be taken at all other times as specified in the Schedule of Activities (SoA) of the protocol. The average of the triplicate measurements will be calculated prior to analyzing the data. Respiratory rate, pulse rate and temperature will be measured at each timepoint specified in the protocol.

Baseline for these measures will be defined as the last pre-dose measurement in each study period.

The following endpoints will be determined:

- Change from baseline in systolic and diastolic BP, pulse rate, temperature, and respiratory rate
- The minimum and maximum post-dose systolic and diastolic BP, pulse rate, temperature, and respiratory rate
- The maximum increase and decrease from baseline over all measurements taken postdose for systolic and diastolic BP, pulse rate, temperature, and respiratory rate values

The maximum increase from baseline will be calculated by selecting the maximum CFB over the respective period, except in the case where a participant does not show an increase. In such an instance, the minimum decrease should be taken. Similarly, the maximum decrease from baseline will be determined by selecting the minimum value of the CFB. In cases where a participant does not show a decrease, the minimum increase should be taken.

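### In fed periods the ECG baseline averages triplicates from before, at the start of and after breakfast, and the order of the meal and the other 0 h assessments is not stated

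*Protocol*

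**What the plan says.** **Meal.** In fed periods, Protocol 5.3.2 (repeated in 6.1.1) has breakfast begin about 30 minutes before the dose: "participants should start breakfast approximately 30 minutes prior to administration of study intervention". It is "consumed over approximately a 20-minute period with study intervention administered approximately 10 minutes after completion of the meal at 0H". The same section requires fasting "approximately 10 hours prior to the collection of the predose PK sample", with no exception for fed periods.

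**Schedule.** Protocol Table 2 is a single Day 1 schedule for every period. It places triplicate ECGs at -1.0, -0.5 and 0 h, and has triplicate BP, the row "Temperature, pulse rate and respiratory rate" and the PK sample at 0 h. Its dosing row mentions food-effect periods; no assessment row is adapted to them. The notes to Table 1 ask only that time-0 activities come before the dose.

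**Baselines.** Protocol 8.3.4 takes as QTcF baseline "the average of the triplicate ECG measurements collected at -1.0, -0.5, and 0 hours pre-dose on Day 1 of each period". Protocol 9.3.1.1 repeats this, and SAP 3.1.5 applies it to all ECG parameters, averaging whichever time points are available. For vital signs, SAP 3.1.3 states: "Baseline for these measures will be defined as the last pre-dose measurement in each study period".

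**Temperature.** Protocol 8.3.3.3 reads: "No eating, drinking, or smoking is allowed for 15 minutes prior to the measurement".

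**Scope.** Fed periods are optional. The protocol foresees them for the crystalline form; SAP version 2 adds a food-effect evaluation of the SDD formulation, analysed from Cohort 3 (SAP 6.2).

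**The concern.** A schedule written for fasted dosing is carried over to fed periods, where breakfast sits inside the ECG baseline window. The fed reference point is then a blend of fasted and post-meal readings. SAP 5.2 treats each fasting state as its own treatment, and SAP 6.1.5 shows changes from baseline by treatment, so fed and fasted changes with different reference points would be set side by side.

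ECG and vital signs belong to the primary safety endpoint. The nonclinical findings in Protocol 2.2.5 include lower BP, shorter QTc, faster heart rate and low body temperature, so these are the measures whose fed reference point is unclear. SAP 5.2 keeps fed placebo out of the placebo pool, which leaves roughly 2 placebo participants per fed period to separate a meal effect from a drug effect.

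There is a smaller consequence. SAP 6.1.3 and 6.1.5 attribute Day 1 pre-dose values that meet the categorical criteria, from Period 2 on, to the preceding treatment. A pre-dose value raised or lowered by breakfast could be counted against the wrong treatment.

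**Working it through.** **1. Meal window (Protocol 5.3.2).** Start -30 min, duration 20 min: end = -30 + 20 = -10 min. Gap to dose = 0 - (-10) = 10 min. This reproduces the protocol's own figure of about 10 minutes.

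**2. ECG time points against the meal (Table 2).**

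| Nominal time | Position | State |
|---|---|---|
| -60 min | 30 min before the meal starts | fasted |
| -30 min | at the start of the meal | meal start |
| 0 min | 10 min after the meal ends | post-meal |

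In a fasted period all three are fasted.

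**3. Weight of the meal in the ECG baseline (SAP 3.1.5, equal weights).** Baseline = (E1 + E2 + E3)/3. Let s be the shift that the meal causes in a triplicate mean.

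- Only the 0 h set is affected: baseline moves by s/3.
- The -0.5 h set slips into the meal and is shifted by as much as s: baseline moves by up to 2s/3.
- The -0.5 h set is missing: baseline = (E1 + E3)/2, so it moves by s/2.
- The 0 h set is missing and the -0.5 h set is unaffected: it moves by 0.

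For scale only, s = 3, 6 or 9 units gives 1, 2 or 3 units (s/3), or 2, 4 or 6 units (2s/3). These values of s are illustrative.

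**4. Room for the ECG sets.** Three readings 2 to 4 min apart span 2 × 2 = 4 to 2 × 4 = 8 min. With at least 5 min supine rest (Protocol 8.3.4) that is 9 to 13 min. The gap after the meal is about 10 min, so the 0 h set may or may not fit.

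**5. Temperature.** At nominal 0 h, 10 min have passed since eating, against 15 min required: 5 min short. The earliest compliant time after the meal is -10 + 15 = +5 min, which is after the dose. A reading before -30 min complies with the rule, is pre-dose, and can serve as baseline under SAP 3.1.3.

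**6. Pre-dose PK sample.** A draw after breakfast breaks the approximately 10-hour fast. A draw before breakfast satisfies both that rule and the Table 1 note.

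**7. ECG heart rate against pulse rate.** With all three ECG sets taken and only the 0 h set affected, the ECG baseline carries s/3. The pulse baseline carries 0 if taken before breakfast, or s if taken after it. The pulse baseline minus the ECG baseline is therefore -s/3 or s - s/3 = 2s/3. Even the sign depends on an order that the documents leave open.

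**The case against.** A reader might infer that no valid pre-dose temperature can be obtained, or that BP, pulse rate and temperature baselines in fed periods must be post-meal. The documents do not support either reading. Time-0 activities need only precede the dose; no window and no order relative to breakfast is set. The PK fasting rule in fact points to a draw before breakfast. Protocol 8.3.3.1 puts BP and pulse rate before the nominal blood-draw time, and 8.1 puts ECGs, BP and pulse rate before any IV catheter is inserted. For these assessments the gap is an unstated order, and that objection stands. So does the point that the 10-minute gap is not shown to be unworkable: 9 minutes fits, and respiratory rate is counted during the rest (8.3.3.2).

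It is also fair that food effect is exploratory with PK endpoints only, that no hypothesis test is planned, and that separate reporting keeps fed data out of the fasted escalation summaries. Protocol 8.5.1 already allows timing changes without an amendment.

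The ECG point survives. Its 0 h set is one of three named time points after -0.5 h. Taking it before breakfast would make it coincide with or precede the -0.5 h set, so following the stated times yields a mixed baseline. A permitted route for changing times does not itself define the fed-period baseline.

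**Conclusion.** The point holds for the ECG baseline and, as an unstated order, for the other 0 h assessments. At nominal times a fed-period ECG baseline combines one fasted, one meal-start and one post-meal triplicate. It carries s/3 of any post-meal shift, and up to 2s/3 if the -0.5 h set falls within the meal. Fed change from baseline is offset by the same amount in the opposite direction; fasted periods have no such offset.

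This rests on the nominal times being followed and on equal weighting of the three time points. A reader might want to express the bias in beats or milliseconds. The documents give no meal effect on heart rate, QTcF, BP or temperature, so only the weighting can be stated. Temperature and PK compliance depend on the site collecting before breakfast, which the text permits but does not require. The reach is limited to optional fed periods, but the measures are part of the primary safety assessment and the correction is cheap.

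**What to change.** Reconcile the meal timing with Table 2 and with Protocol 5.3.2 (PK fast), 8.3.3.3, 8.3.4 and 9.3.1.1. Add a fed-period footnote to Table 2, and matching text in 8.3.4, 9.3.1.1 and SAP 3.1.3 and 3.1.5. These should state that in fed periods all baseline ECG triplicates, the baseline vital signs including temperature, and the pre-dose blood samples are completed before breakfast starts, and that these readings form the period baseline. ECG sets at nominal -1.5, -1.0 and -0.75 h would be one way to do it.

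The cost is a footnote and a few sentences, plus an earlier start for staff; in that example the first ECG set moves 30 minutes earlier. There are two statistical costs. Baseline ECG clock times would differ slightly from those in fasted periods. The fed change from baseline would also carry the full meal effect and would have to be read against the roughly 2 fed-placebo participants. In return, fed and fasted periods share a fasted reference point, and the fed-placebo group shows the meal effect openly.
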